#### **8.1.4. Timing of Analyses**

All final, planned analyses will be performed after the last participant has completed all study assessments, all relevant study data have been processed and integrated into the analysis database, and the database has been locked.

Any post-hoc, exploratory analyses completed to support planned study analysis, which were not identified in this SAP, will be documented and reported in appendices to the CSR. Any results from these unplanned analyses (post-hoc) will also be clearly identified in the text of the CSR.

#### **8.1.5. Multiple Comparisons/Multiplicity**

The overall type I error rate will be controlled at  $\alpha=0.05$  for the set of primary and key secondary endpoint comparisons between each dose level of active versus placebo using a graphical approach. Each of the dose comparisons to placebo will be assigned  $\frac{1}{2}$  the alpha for the primary endpoint of change in the number of migraine headache days from the last 28 days of Baseline to the last 28 days of treatment. The stronger of the p-values will be tested first at  $\alpha=0.025$  and if significant, 100% of its alpha will be passed to the other dose’s primary comparison so that it is tested at  $\alpha=0.05$ .

If this is significant, then this  $\alpha=0.05$  will be passed to the first secondary and split for the two dose comparisons to placebo on the endpoint of the proportion of patients experiencing a  $\geq 50\%$  reduction in the number of migraine headache days from Baseline to month 3. As above, the stronger of the p-values will be tested first at  $\alpha=0.025$  and if significant, 100% of its alpha will be passed to the other dose’s secondary endpoint comparison ( $\alpha=0.05$ ). At each step, if a p-value fails to meet the alpha threshold for significance, the process will be halted and all subsequent comparisons declared non-significant. This will continue with the same pattern through the endpoints in the order listed below:

The order of the key secondary analyses will be:

- Proportion of patients experiencing a  $\geq 50\%$  reduction in the number of migraine headache days from the last 28 days of Baseline to the last 28 days of treatment in each treatment group.
- Mean change in the number of days using rescue medication (triptan, ergot derivative, or other migraine-specific acute medication) from the last 28 days of Baseline to the last 28 days of treatment.
- Proportion of patients with a Patient Global Impression of Change (PGIC) rating of 1, “very much improved”, or 2, “much improved”, at Week 12.

- Mean change in the number of moderate or severe headache days from the last 28 days of Baseline to the last 28 days of treatment. A moderate or severe headache day is defined as any calendar day wherein a patient records a headache of moderate or severe peak intensity in the e-diary.
- Mean change in the number of migraine headache days from the last 28 days of Baseline to average number per 28 days over the entire 12 week duration of Treatment Period.
- Mean change from Baseline in the Migraine-Specific Quality of Life Questionnaire Role Function, Restrictive domain (MSQ v2.1) at Week 12.

The order of the other secondary analysis will be:

- Mean change from Baseline in the Migraine Disability Assessment (MIDAS) Test total score at Week 12.
- Mean change from Baseline in the Hospital Anxiety and Depression Scale (HADS) total score at Week 12.
- Mean change from Baseline in patient-rated Changes in Sexual Functioning Questionnaire Short-Form (CSFQ-14) total score in males and in females, analyzed separately, at Week 12.

The exploratory analyses will be:

- Proportion of patients experiencing a  $\geq 75\%$  reduction in the number of migraine headache days from the last 28 days of Baseline to the last 28 days of treatment in each treatment group.
- Proportion of patients with fewer than 14 headache days or fewer than 8 migraine headache days per 4 weeks over the 12-week period.
- Mean change from Baseline in number of headache free days from the last 28 days of Baseline to the last 28 days of treatment

Although all p-values will be non-significant following the first to fail to meet its alpha threshold, p-values will be reported for all the above endpoints; they will be noted as descriptive for those following the first non-significant p-value.

#### **8.1.6. Power and Sample Size**

The planned total number of randomized patients is approximately 300 and will be randomized 1:1:1 to TNX-1900 30 IU QAM, placebo QPM: TNX-1900 30 IU BID: or placebo BID. [REDACTED]

[REDACTED]

[REDACTED]

[REDACTED]

Tonix Pharmaceuticals  
Statistical Analysis Plan: TNX-OX-CM201

[REDACTED]

[REDACTED]

## 9. ENDPOINT EVALUATION

### 9.1. Primary Endpoint

The primary efficacy endpoint will be the change in the number of migraine headache days from the last 28 days of Baseline to the last 28 days of treatment (i.e. month 3). A migraine headache day is any calendar day (0:00 to 23:59) in which the patient records in the e-diary:

- An attack lasting 4 hours or more and meeting the ICHD-3 criteria for migraine without aura, or
- A migraine with aura, or
- An attack that meets ICHD-3 criteria for probable migraine (a migraine subtype fulfilling all but one criterion (B-D) for migraine without aura), or
- An attack of any duration that was believed by the patient to be a migraine and was relieved by a triptan, ergot derivative, or other migraine-specific abortive medication (see Appendix 15.5)

#### 9.1.1. Computation of the Primary Endpoint

The monthly migraine count will be calculated for patients that have at least 14 days of non-missing data for a given month. For patients with less than 28 days of data for a month, the counts will be normalized to 28 days by taking  $28 * [\text{migraine count}] / [\text{days of non-missing data}]$ . The eDiary questions and derivation of migraine days are found in [Appendix 15.4](#).

If less than 14 days are available for a month, then the month will remain missing, but the patient's other months will contribute to the estimation via a mixed-effects model of repeated measures.

Every effort will be made to retain patients in the study; however, patients are free to withdraw from the study at any time for any reason. Patients that withdrawal early will be asked to return to the clinic for an Early Termination Visit for completion of assessments (see Schedule of Assessments). The mixed model repeated measures analysis will provide unbiased estimates under the assumption that data are missing at random (MAR).

#### 9.1.2. Primary Analysis of the Primary Endpoint

Summary statistics (mean, SD, median, minimum, maximum) for the primary efficacy endpoint will be reported for the change from the Baseline to month 3 for each of the treatment groups. The change from Baseline will be analyzed in an MMRM model with fixed effects of treatment, month, baseline value, treatment by month interaction, and stratification factor (preventive medication use); an unstructured covariance matrix will be used. Least square means (LSMs), standard errors, and the LSM differences (each treatment vs placebo) with 95% CIs and p-values will be reported for each month. Denominator degrees of freedom will use the Kenward Rogers approach. Should the model fail to converge, heterogeneous Toeplitz, heterogeneous first-order autoregressive, Toeplitz, first order autoregressive and compound symmetric will be attempted in that order; in these cases, the sandwich estimator (Diggle and Kenward 1994) will be used to

estimate the standard errors of the fixed effects parameters and the denominator degrees of freedom will utilize the DDFM=BETWITHIN option in SAS®.

Additionally, Kruskal-Wallis tests will be performed and reported for each month, in case the migraine days do not adhere to model assumptions.

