# **10.2** Determination of Sample Size

The planned total number of randomized patients is approximately 300 and will be randomized 1:1:1 to TNX-1900 30 IU QAM, placebo QPM: TNX-1900 30 IU BID: or placebo BID. The sample size estimate was derived using a two-sided t-test with 90% power and 5% two-sided significance level to test the primary efficacy statistical superiority hypothesis of TNX-1900 30 IU BID over placebo.

Based on a post-hoc analysis of a chronic migraine subgroup from a prior study, it is anticipated that a difference in mean change from Baseline to study end (last 28 days of double-blind) in migraine headache days between TNX-1900 30 IU BID and placebo BID would be approximately 1.84 with a common standard deviation of  $\pm$  3.95. As such the required sample size per group is approximately 100.

Accounting for the multiplicity adjustment by applying an alpha of 2.5% to the first test yields power of approximately 85% with the above assumptions.

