## 10.7.2 Efficacy Analysis

#### 10.7.2.1 Primary Efficacy Analysis

Summary statistics (mean, SD, median, minimum, maximum) for the primary efficacy endpoint will be reported for the change from the Baseline to month 3 for each of the treatment groups. The change from Baseline will be analyzed in a Mixed-Effects Model of Repeated Measures (MMRM) model with fixed effects of treatment, month, baseline value, treatment by month interaction, baseline by month interaction, site, and stratification factor (preventive medication use); an unstructured covariance matrix will be used. Least square means (LSMs), standard errors, and the LSM differences (each treatment vs placebo) will be reported for each month. Denominator degrees of freedom will use the Kenward Rogers approach. Should the model fail to converge, heterogeneous Toeplitz, heterogeneous first-order autoregressive, Toeplitz, first order autoregressive and compound symmetric will be attempted in that order; in these cases, the sandwich estimator (Diggle and Kenward 1994) will be used to estimate the standard errors of the fixed effects parameters and the denominator degrees of freedom will utilize the DDFM=BETWITHIN option in SAS®.

To account for the blinded interim sample size re-estimation (Section 10.8), data from the interim and post-interim cohorts will be combined using the inverse normal method to test

the null hypotheses that there is no difference in the change from Baseline to month 3 in number of migraine days per month between each of the active groups and placebo (Cui et al 1999):

$$Z_1 = \Phi^{-1}(1 - p_1)$$
 (1)  
and  $Z_2 = w_1 Z_1 + w_2 \Phi^{-1}(1 - p_2)$ 

Where:

 $Z_1$  = the Z statistic for the first stage

 $Z_2$  = the combination test statistic at the end of the second stage

wi = the weighting applied for each associated Z statistic

 $p_1$  = the first stage p-value

p2 =the second stage p-value based on second stage participants

The weights are defined prospectively according to the square-root of the planned proportion of participants in the two stages, relative to the preplanned total enrollment of 300 participants, as  $w_i = \sqrt{0.5}$ . In order to control the type-I error, adaptive changes of the stage wise sample sizes will not lead to changes of the weights (Lehmacher and Wassmer 1999).

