# 10.7.2.2 Sensitivity Analyses

Three sensitivity analyses will be performed:

- Multiple imputation methodology will be utilized to impute complete datasets with three monthly observations for all patients in the mITT population. This will be done within each treatment group conditioned on each patient's non-missing data (including baseline), site, and the stratification factor.
- A tipping point analysis will be performed using the above MI datasets and applying an increasing penalty to the active group until statistical significance is no longer achieved.
- Finally, a missing-not-at-random multiple imputation approach will be utilized taking into account the reason for discontinuation; intermittent missing data will still be assumed to be missing at random.

Full details of each analysis will be provided in the SAP.

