### 7.2. Randomization

This is a double-blind study; unless otherwise specified, all study personnel are to remain blinded to study drug prior to database lock and final analysis following study unblinding.

Approximately 300 eligible patients will be randomized at a 1:1:1 ratio, to one of the 3 treatment arms receiving TNX-1900 at a fixed daily dose of 30 IU QD (Treatment Arm A) or fixed daily dose of 30 IU BID (Treatment Arm B) or receiving placebo (Treatment Arm C) for the duration of a 12-week Treatment Period. Randomization will be stratified by site and use of one concomitant preventive migraine medication (vs. no concomitant preventive migraine medication). All participants will administer study drug twice a day, mornings and evenings, in a double-blind design. Up to approximately 30% of the patients randomized into the study can be on 1 migraine preventative medication.

The randomization schedule will be computer generated using a permuted block algorithm and will randomly allocate study drug to randomization numbers. The randomization numbers will be assigned through a central interactive web response system (IWRS) as patients are entered into the study.

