### **8.1.2. Multicenter Studies**

This is a multicenter study. Unless otherwise specified, data from all study sites will be pooled for all analyses unless otherwise specified.

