#### **9.1.3.1. Missing at Random Multiple Imputation**

Multiple imputation (MI) methodology will be utilized to impute complete datasets with three monthly observations for all patients in the mITT population. Monthly migraine counts will be computed as described in Section 9.1.1. This will yield 4 migraine count records per patient (baseline and 3 months follow-up). The missing values will be imputed for all patients/records using MI within each treatment group conditioned on each patients' non-missing data (including baseline), and the stratification factor. The Markov Chain Monte Carlo (MCMC) method will be used to produce 20 repeats of the data and seeds are given in [appendix 15.2](#). LS means and differences across the twenty MI reps will be combined using SAS procedure MIANALYZE ([Rubin, 1976](#)).

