### **9.2.2. Additional Secondary Endpoints**

Each of the following continuous endpoints will be summarized:

- Mean change from Baseline in the Hospital Anxiety and Depression Scale (HADS) at Week 12.
- Mean change from Baseline in the Migraine Disability Assessment questionnaire (MIDAS) Test total score at Week 12.
- Mean change from Baseline in patient-rated Changes in Sexual Functioning Questionnaire Short-Form (CSFQ-14) total score in males and in females, analyzed separately, at Week 12.

For each, summary statistics (mean, SD, median, minimum, maximum) will be reported for the change from the baseline to each visit and for each of the treatment groups.

For HADS the change from baseline will be analyzed in an MMRM model with fixed effects of treatment, visit, baseline value, treatment by visit interaction, and stratification factor (preventive medication use); an unstructured covariance matrix will be used. LSMS, standard errors, and the LSM differences (each treatment vs placebo) with 95% CIs and p-values will be reported for each visit (with week 12 being of primary interest). Denominator degrees of freedom will use the Kenward Rogers approach. Should the model fail to converge, heterogeneous Toeplitz, heterogeneous first-order autoregressive, Toeplitz, first order autoregressive and compound symmetric will be attempted in that order; in these cases, the sandwich estimator (Diggle and Kenward 1994) will be used to estimate the standard errors of the fixed effects parameters and the denominator degrees of freedom will utilize the DDFM=BETWITHIN option in SAS®.

MIDAS and CSFQ are only collected at baseline and week 12, thus they will be modeled in a ANCOVA similar to the MMRM used for the repeated measures. The model will include fixed effects for treatment, baseline, and stratification factor (preventive medication use). LSMS, standard errors, and the LSM differences (each treatment vs placebo) with 95% CIs and p-values will be reported.

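### The SAP's primary MMRM leaves out site, a randomisation factor that the protocol's primary model includes; if sites differ, the primary test is conservative

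*SAP*

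**What the plan says.** SAP 7.2 names two stratification factors: "Randomization will be stratified by site and use of one concomitant preventive migraine medication". Protocol 5.3 names the same two. Both documents use permuted blocks.

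Protocol 10.7.2.1 carries both factors into the primary MMRM, whose listed terms end with "baseline by month interaction, site, and stratification factor (preventive medication use"). SAP 9.1.2 lists "fixed effects of treatment, month, baseline value, treatment by month interaction, and stratification factor (preventive medication use"). Site and the baseline-by-month term are missing, and the stratification factor has become singular.

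The same gap runs through the rest of the SAP:

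- The MSQ MMRM (9.2.1.4) and the HADS MMRM (9.2.2) have no site term.
- For the MIDAS and CSFQ-14 ANCOVAs, 9.2.2 says "The model will include fixed effects for treatment, baseline, and stratification factor (preventive medication use").
- Imputation in 9.1.3.1 is "conditioned on each patients' non-missing data (including baseline), and the stratification factor", whereas protocol 10.7.2.2 conditions on "non-missing data (including baseline), site, and the stratification factor".
- SAP 8.1.2 says that "data from all study sites will be pooled for all analyses unless otherwise specified", and 9.1.2 does not specify otherwise.

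SAP section 13, which lists changes from the protocol, is redacted. Whether this change is declared or justified there cannot be seen.

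**The concern.** Stratified randomisation balances the arms within each site, so differences between sites largely cancel out of the treatment comparison. A model without site does not credit that cancellation and leaves the between-site variance in the residual. If sites differ in outcome, the reported SE exceeds the true one, confidence intervals are too wide, and the test rejects less often than its nominal level.

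The cost is precision, on the test where it matters most. Under SAP 8.1.5 both doses must succeed on the primary endpoint before any alpha reaches the key secondary endpoints, and one failure stops the sequence. The SAP's sensitivity analyses of the primary endpoint (9.1.3) address missing data only, so none fills the gap. As they stand, the protocol and the SAP also specify two different primary models.

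**Working it through.** **Inputs.** From protocol 10.2: difference 1.84, SD 3.95, 100 per arm, alpha 0.025 for the first test. From the protocol synopsis: about 25 sites. Assumed, because the documents give no value: the site share of residual variance, ρ = 0, 0.02, 0.05 or 0.10.

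**The plan's own figures.** Protocol 10.2 sizes the trial with a "two-sided t-test with 90% power and 5% two-sided significance level". A noncentral t calculation gives 98 per group (97 by the normal approximation), against about 100 stated. With 100 per group and alpha 0.025, power is 84.9% (85.4% normal), against about 85% stated. Both reproduce.

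**Closed form, arms exactly balanced within site.**

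- Reported SE = 3.95 × √(2/100) = 0.5586.
- True SE = 0.5586 × √(1−ρ).
- Overstatement factor k = 1/√(1−ρ).
- Actual two-sided alpha = 2(1−Φ(2.2414k)).
- Power with site omitted = P(T > k × t_crit), where T is noncentral t with noncentrality 1.84/(true SE) and 295 df.
- Power with site included: same noncentrality, unscaled critical value, 271 df (24 fewer for 25 sites).

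| ρ | True SE | SE overstated | Actual alpha | Power, site omitted | Power, site included |
|---|---|---|---|---|---|
| 0 | 0.559 | 0% | 0.025 | 85.0% | 85.0% |
| 0.02 | 0.553 | 1.0% | 0.024 | 85.3% | 85.8% |
| 0.05 | 0.544 | 2.6% | 0.021 | 85.7% | 86.9% |
| 0.10 | 0.530 | 5.4% | 0.018 | 86.3% | 88.8% |

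**Incomplete blocks.** About 25 sites × 2 preventive strata gives about 50 cells for 300 patients, or 6 per cell, so many blocks stay unfilled and balance is imperfect. Allocations were simulated (1,200 to 3,000 per setting) with unequal site sizes, 30% on a preventive, and blocks of 3 or 6 within site × preventive stratum. Site sizes and block sizes are assumed. Alpha below comes from putting each overstatement into the formula above as k.

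| ρ | SE overstated | Actual alpha | Power change, site unpooled (points) | Power change, sites under 12 patients combined (points) |
|---|---|---|---|---|
| 0 | 0% | 0.025 | −0.7 to −1.1 | −0.1 to −0.2 |
| 0.02 | 0.8% | 0.024 | −0.1 to −0.5 | +0.2 |
| 0.05 | 2.0-2.2% | 0.022 | +0.3 to +0.7 | +0.7 to +0.8 |
| 0.10 | 4.0-4.5% | 0.019-0.020 | +1.7 to +1.9 | +1.6 to +1.7 |

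Combining small sites left 11.8 site groups on average. In 10-15% of sites at least one arm was empty.

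**Independent check.** Simulated Month 3 trials (6,000 per null setting, nominal 2.5% test) without site rejected in 2.2-2.5% at ρ = 0.05 and 1.8-2.1% at ρ = 0.10. With site in the model the rates were 2.2-2.8%. Monte Carlo error is about √(0.025 × 0.975/6000) = 0.2 points.

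**Baseline-by-month.** With an assumed slope difference of 0.1 and baseline SD of 4, the omitted term is (0.1 × 4)²/3.95² = 1.0% of variance, or about 0.5% of the Month 3 SE. That is negligible for power.

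**The case against.** The best opposing case is that nothing invalid results. The estimate is unbiased, type I error is not inflated, and the sizing used an unadjusted t-test, so the SAP model still delivers the planned power. All of that stands. What is forgone is a possible gain.

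The gain also rests on an assumed variance share. Baseline adjustment may already absorb part of any site difference, and only what remains counts. Restoring the protocol's model exactly as written, with about 25 unpooled sites, would lose a little power at shares of 0% and 2%. This stands too. It is a reason to combine small sites rather than to drop site altogether.

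The exact-balance figures are upper bounds on the conservatism. That is correct, and the incomplete-block table is the better guide.

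Finally, the omission is consistent across models and may be deliberate and explained in the redacted section 13. For that reason it should not be called undeclared. It does not alter the fact that no analysis visible in the SAP adjusts the primary endpoint for site.

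**Conclusion.** The concern holds. Site is a randomisation factor and a term in the protocol's primary model, and it is absent from the SAP's primary model, its other continuous-endpoint models and its imputation model. If outcomes differ between sites, the primary test is conservative.

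The effect is modest. At an assumed site share of 10%, the SE is overstated by 4.0-4.5% with realistic allocation, and pooled site adjustment gains 1.6-1.7 power points. At 5% the gain is 0.7-0.8 points, and at 0% it is a loss of 0.1-0.2. The direction is firm; the size depends on assumed between-site variance, site sizes and block sizes. The change should be made, but the trial's validity does not depend on it.

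**What to change.** In SAP 9.1.2, restore site as a fixed effect in pooled form, with the rule set before unblinding: for example, combine sites with fewer than 12 mITT patients. Naming site there already satisfies the exception in 8.1.2, but a line in 8.1.2 stating that pooled site is a covariate would prevent misreading.

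Carry the same term into the MMRMs for the continuous diary endpoints, MSQ and HADS, and into the MIDAS and CSFQ-14 ANCOVAs. In 9.1.3.1 use site only in pooled form, because imputation runs within arms of about 100 patients. Restore baseline-by-month to align the wording with the protocol. The CMH tests need no change, since protocol 10.7.2.3 also stratifies them by preventive use alone.

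If site was left out on purpose, the SAP should give the reason, unless section 13 already does, and name the site-adjusted MMRM as a sensitivity analysis.

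The cost is SAP wording plus one pooling rule that the protocol does not contain. It uses about 11 degrees of freedom under the assumed site sizes, against up to about 24 unpooled. If sites do not differ, the price is about 0.1-0.2 power points pooled and up to about 1.1 unpooled.

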##### **9.1.4.2. Patients Experiencing a $\geq 50\%$ Reduction in Migraine Headaches**

Finally, for each patient and month, patients will be flagged as responders if they experience a  $\geq 50\%$  reduction in the number of migraine headache days from the last 28 days of Baseline to the given month's 28-day normalized migraine headache days. The percent change from baseline will be calculated for each month as  $100 * [\text{monthly count} - \text{baseline count}] / [\text{baseline count}]$ . The number and percentage of patients achieving  $\geq 50\%$  improvement will be reported as well as 95% CIs for the percentages. Patients with missing data will be considered non-responders/ not achieving either improvement threshold. The difference in percentages in the active and placebo arms from the Cochran-Mantel-Haenszel (CMH) common risk difference estimator will be reported along with its 95% CI based on the Sato variance estimator. Pairwise p-values will compare each treatment arm to placebo based on a CMH stratified by preventive medication use. The primary time point of interest will be month 3, but each month will be summarized.

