#### 9.2.1.1. Rescue Medication Use

The Mean change in the number of days using rescue medication from the last 28 days of Baseline to the last 28 days of treatment will be compared among the treatment groups. A rescue medication use day is any calendar day (0:00 to 23:59) in which the patient records the use of a triptan, ergot derivative, or other migraine-specific abortive medication (see Appendix 15.5). Calculation and analysis of this will be identical to the primary with the substitution of days using rescue medication for migraine days. Least square means (LSMs), standard errors, and the LSM differences (each treatment vs placebo) will be reported for these averages. As with the primary endpoint, Kruskal-Wallis tests will be performed and reported.

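### The rank-based back-up to the MMRM is an unadjusted Kruskal-Wallis test with its arms unstated; an adjusted dose-versus-placebo rank test would answer the trial's question at almost no cost

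*SAP*

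**What the plan says.** SAP 9.1.2 fits an MMRM to the change in migraine days, adjusted for the baseline value and for preventive-medication use. The planned output is pairwise: "LSM differences (each treatment vs placebo) with 95% CIs and p-values will be reported for each month". The section then adds that "Kruskal-Wallis tests will be performed and reported for each month, in case the migraine days do not adhere to model assumptions".

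The visible text does not say which arms enter the test, whether the variable is the change or the monthly count, what estimate goes with it, or what follows if it disagrees with the MMRM. SAP 8.1.1 (Study Success) and SAP 13 are redacted, so a rule stated there cannot be excluded.

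The test is reused for rescue-medication days in SAP 9.2.1.1 ("As with the primary endpoint, Kruskal-Wallis tests will be performed and reported"), for moderate or severe headache days in 9.2.1.3 and for headache-free days in 9.2.3. Protocol 10.7.2 does not mention it.

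Two other places show what the plan is trying to test. In SAP 8.1.5, "Each of the dose comparisons to placebo will be assigned" half the alpha for the primary endpoint, and the whole hierarchy runs on those two comparisons. For the 50% responder endpoint, SAP 9.1.4.2 is explicit: "Pairwise p-values will compare each treatment arm to placebo based on a CMH stratified by preventive medication use". The Kruskal-Wallis sentence has no such wording.

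**The concern.** Every confirmatory hypothesis is one dose against placebo. A three-arm Kruskal-Wallis test asks whether three distributions are equal. It can reject because the two doses differ from each other, and it can miss when only one contrast is large.

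Even on the two-arm reading, the test removes the baseline and stratum adjustment at the same moment as it removes the normality assumption. It also omits any patient whose month is missing, whereas the MMRM uses that patient's other months. If the two analyses disagree, nobody can tell whether the cause is skewed counts, lost adjustment, missing months or the QD-BID contrast. A check meant to isolate one departure from assumptions then changes several things at once and returns only a p-value. If the text allows both readings, the choice between them could also be made after unblinding.

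**Working it through.** **Inputs from the documents.** BID-placebo difference 1.84 and SD 3.95 (Protocol 10.2); 300 randomised 1:1:1; 265 expected to complete (Protocol Figure 1), so 265/3 ≈ 88 per arm; about 30% at most on a preventive (Protocol 4.1, criterion 4); first-step alpha 0.025 (SAP 8.1.5).

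**Assumed, because the documents do not give them.** The QD effect, the correlation between baseline and change, and normal change scores. In the simulations preventive use had no effect on outcome, so any gain from adjustment comes from the baseline count.

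**Step 1: the plan's own figures.** Protocol 10.2 says "The sample size estimate was derived using a two-sided t-test with 90% power and 5% two-sided significance level", with a difference that "would be approximately 1.84 with a common standard deviation of" 3.95.

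n = 2 × (3.95/1.84)² × (1.960 + 1.282)² = 2 × 4.608 × 10.51 ≈ 97 per arm (98 with the exact t), against about 100 stated.

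Power at 0.025 with 100 per arm: 1.84/(3.95 × √(2/100)) = 3.294; Φ(3.294 − 2.241) = 85.4% (exact t 84.9%), against about 85% stated. Both reproduce.

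**Step 2: what the test contains.** H = 12/[N(N+1)] × Σ(Rⱼ²/nⱼ) − 3(N+1), where Rⱼ is the rank sum of arm j. With three arms it is referred to chi-square on 2 df and includes the QD-BID contrast. With two arms it is the Wilcoxon test. Neither form has a baseline or stratum term.

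**Step 3: simulation.** Change = −effect − ρ × 3.95 × b + 3.95 × √(1 − ρ²) × e, with b and e standard normal; 4,000 trials per scenario; Monte Carlo standard error at most √(0.25/4000) = 0.8 points. The adjusted rank test takes one dose and placebo, ranks change and baseline, regresses the change ranks on baseline ranks and stratum, and compares residuals between arms. The data are normal by construction, so any disagreement seen here cannot be due to non-normality.

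With 88 per arm, BID 1.84, QD 0.92 and ρ = 0.45:

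| Test | Power at 0.05 | Power at 0.025 |
|---|---|---|
| Three-arm Kruskal-Wallis | 76% | not applicable |
| BID vs placebo, unadjusted rank-sum | 85% | 76% |
| BID vs placebo, rank ANCOVA | 91% | 86% |

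At a common 0.05, the change of contrast accounts for 85 − 76 = 9 points and the adjustment for 91 − 85 = 6. The plan, however, tests the stronger dose first at 0.025. On that footing the change of contrast is worth 76 − 76 = 0 and the adjustment 86 − 76 = 10.

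The adjustment gain depends on ρ. With 100 per arm and ρ = 0, 0.3 and 0.5, rank ANCOVA power for BID at 0.05 is 89%, 91% and 96%, against about 89 to 90% unadjusted throughout. Its type I error was 4.3 to 5.0% at nominal 5%.

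**Step 4: other QD effects.** With 88 per arm, when QD is null or equals BID, omnibus power is 88 to 89%, close to the adjusted test at 0.05 (about 91%).

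**Step 5: disagreement with the primary.** A baseline-adjusted ANCOVA stood in for the MMRM at month 3. With QD 0.92 and BID 1.84, at least one dose was positive at 0.025 while Kruskal-Wallis was non-significant in 14% of trials (88 per arm, ρ = 0.45). With 100 per arm it was 4.6%, 7.8% and 13.2% for ρ = 0, 0.3 and 0.5.

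**Step 6: stress case.** QD is 0.92 worse and BID 0.92 better than placebo. Kruskal-Wallis is significant in about 78% of trials and BID beats placebo (rank-sum at 0.05) in about 32%. So it must be significant with no winning dose in at least 78 − 32 = 46%, within simulation error. The direct count is about 47% (45 to 47% over repeat runs). It falls to 19% if trials with a dose significantly worse than placebo are excluded.

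**The case against.** Four points on the other side carry weight.

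First, a reader might infer that the SAP prescribes a three-arm test. It does not say so. It writes of tests in the plural, directly after contrasts of each treatment with placebo, and a two-group Kruskal-Wallis would test dose versus placebo. The three-arm reading is the natural one for this test in a three-arm trial, but it is an inference. This stands. What survives on both readings is the lost adjustment and the missing estimate.

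Second, a reader might infer that nothing else in the plan gives a check free of normality. SAP 9.1.4.2 does: a stratified, pairwise CMH on the responder proportion at month 3, with a risk difference and interval, first among the key secondaries. It is directional and relative to each patient's baseline. It dichotomises the outcome, so it covers the gap only in part.

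Third, the test is additional. It replaces nothing, has no place in the alpha plan of SAP 8.1.5, and no visible rule lets it overturn the MMRM. This stands and limits the seriousness.

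Fourth, it is tempting to say that the omnibus form itself costs power. At the plan's first-step alpha it does not, and when QD is null or equal to BID it performs well. The stress case needs QD to be harmful, which nothing in the documents suggests.

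**Conclusion.** The point holds as a matter of specification and method. SAP 9.1.2 leaves the arms, variable and estimate of its distributional back-up open. As written, the test lacks the adjustment that the MMRM has, so a discordant result could not be attributed to non-normality.

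The size depends on the scenario. With a graded dose response and a correlation of 0.45, an adjusted rank test for BID has about 10 points more power than either the omnibus test at 0.05 or the unadjusted pairwise test at 0.025. The gain vanishes if baseline and change are uncorrelated, and the correlation is an assumption. The 47% is a stress figure that shows what an omnibus p-value cannot tell the reader; it is not an expectation for this trial.

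The documents do not support reading this as a flaw in the primary analysis or a threat to type I error. It is an inexpensive improvement that should be made.

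**What to change.** In SAP 9.1.2, 9.2.1.1, 9.2.1.3 and 9.2.3, replace Kruskal-Wallis with a rank ANCOVA of each dose versus placebo on the change from baseline, adjusted for the baseline count of the endpoint concerned and preventive use. Make month 3 of primary interest and label the analysis supportive.

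Report a location-shift estimate with a 95% CI. If it is the ordinary Hodges-Lehmann interval, label it unadjusted, since it can differ from the rank ANCOVA p-value. Do not offer van Elteren as an equivalent: it stratifies but does not adjust for the baseline count. Say that patients with a missing month 3 are left out of the rank test, and how a result that disagrees with the MMRM will be described.

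The cost is a few sentences of SAP text and a short program, settled before unblinding. The primary model, alpha plan and sample size do not change.
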